#### *7.1.1.1 Treatment arm 1: Standard support (SS)*

All participants in the trial will be prescribed acamprosate (two 333mg tablets morning, afternoon and evening or two 333mg tablets in the morning and one 333mg tablet in the afternoon and evening if the service users body weight is below 60kg) as soon as possible following alcohol abstinence in addition to the psychosocial care normally provided. The decision to initiate acamprosate will be determined by the treating clinician in the specialist alcohol service in conjunction with the service user.

The NICE guideline on diagnosis, assessment and management of harmful drinking and alcohol dependence (13) recommends, "Service users taking acamprosate should stay under supervision, at least monthly, for 6 months, and at reduced but regular intervals if the drug is continued after 6 months" p426. In clinical practice, after completion of assisted alcohol withdrawal, service users remain under the care of the specialist alcohol service for up to three months before they are transferred back to the care of their GP for ongoing care including prescribing. The type, frequency and intensity of psychosocial intervention received vary between specialist alcohol services and between individual service users, dependent on their needs, local funding and services available. As this is a pragmatic RCT, SS will be the care normally provided by local participating services, and service use will be recorded for each participant. However, participating services have agreed to follow the NICE guideline with respect to acamprosate prescribing with trial participants. Based on the current service provision of the five proposed study centres, SS is monthly pick up of prescribed acamprosate from the community pharmacy and monthly monitoring of the service user for three months by the specialist alcohol service and then returned to the care of their GP for monthly monitoring in accordance with the NICE guidelines (13) and current NHS clinical practice. As the trial is pragmatic it will be possible for patients to continue being prescribed acamprosate beyond the 24 week period of medication adherence monitoring providing this is agreed between patients and clinicians, in accordance with NICE guidelines.

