#### 7.1.9 Randomisation

The proposed trial involves differential allocation of the order of 2:1:1 to maximize the utility of resources with twice as many being allocated to the SS group than the intervention groups. Randomisation will be carried out after consent has been gained and the initial baseline assessment has been conducted. A remote randomisation procedure will be used through an online system developed and maintained by Codeface Ltd to generate the treatment allocation, which will be initiated by a trained researcher. It is not possible for participants and the study team to be blind to treatment allocation. Allocation will employ a stratified random permuted block method with stratification by severity of alcohol dependence (SADQ score of  $\leq 30$  or  $>30$ ), site and the prescription of other relapse prevention medication. These variables are known to be related to clinical outcomes and will be collected at preliminary screening.

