### 7.2.4 Data analysis

In the main trial the primary outcome measure is percent prescribed medication taken at 24 weeks post-randomisation assessed using a triangulation method. After checking for distributional assumptions and employing necessary transformations, an initial multiple analysis of covariance will be undertaken using a mixed model approach addressing the observed differences between SS versus SS+MM versus SS+MM+CM. If this analysis provides evidence of effect a second analysis of covariance will explore the differences of SS versus SS+MM and SS versus SS+MM+CM. Covariates included in the analysis will include stratification variables, gender and body weight (<60kg or 60+ kg). Mean differences between the groups will be presented with associated 95% confidence intervals. Multiple imputation will be employed to address the nature of missing data and sensitivity analysis will address the influence of missing data on the observed outcome. Secondary analysis will address drinking outcomes at 6 and 12 months using appropriate modelling approaches and these will be adjusted for known confounders; SADQ, site, age and gender. Time to relapse and relapse to heavy drinking will be assessed using survival analysis. Further secondary analyses will explore adherence data at 12 months. We will explore the association between adherence and drinking outcomes using a linear regression adjusted for known confounders and include an adherence\*allocation interaction term. As with most trials the analysis plan will be refined throughout the course of the study and the final analysis plan prepared and agreed by the research team and Trial Steering Committee.

Further analysis will be conducted to identify interactions between variables, including ratings of therapeutic relationship, and fidelity of MM and CM delivery, on clinical and adherence outcomes. The analysis will be governed by an explicit data analysis plan agreed in advance by the Trial Steering Committee.

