### 7.2.5 Economic analysis

The economic evaluation will compare the costs and effects of SS+MM+CM and SS+MM compared to SS alone for adherence to acamprosate prescribed for alcohol dependence. The primary analysis will compare costs and cost effectiveness at 12 month follow up of (a) SS compared to SS+MM, and (b) SS compared to SS+MM+CM, in line with primary aims of the study. Secondary analyses will explore SS compared to SS+MM compared to SS+MM+CM in a three-way comparison. The primary economic perspective will be the health and social care provider (NHS/PSS). Broader patient and societal perspectives will be considered in sensitivity analysis (i.e. criminal justice contacts and criminal activity, patient travel costs). A cost-utility analysis will be conducted using quality-adjusted life-years (QALYs) based on the EQ-5D-5L, a more sensitive version of the EQ-5D, that is a measure of health-related quality of life extensively used in previous alcohol studies in the UK (e.g. UKATT Research Team (93)). QALYs will be calculated by estimating the area under the curve between each consecutive follow up point. Patient-level resource use will be collected using the Adult Service Use Schedule (ADSUS) modified for alcohol misuse (94) and treatment adherence from clinical records. The ADSUS includes items on the cost of crime. Resource use will be valued

using national tariffs (PSSRU, NHS National Reference Costs). Costs and QALYs will not be discounted as the trial time horizon is 12 months. Costs and QALYs will be adjusted for pre-specified baseline covariates (age, gender, alcohol dependence severity) including costs and utility values using generalised linear modelling methods. Missing cost and QALY data will be imputed using multiple imputation methods. Cost-effectiveness will be assessed by estimating incremental cost-effectiveness ratios (ICERs) (95). Interventions with ICERs below £20,000 per additional QALY are generally considered cost-effective by NICE. Decision uncertainty around cost and effectiveness estimates will be represented by cost-effectiveness acceptability curves (CEACs) generated using non-parametric bootstrap methods to account for non-normal joint distributions of costs and outcomes (96).

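### The pre-specified covariates for the cost and QALY models leave out two of the three randomisation strata, so the economic intervals may be slightly wider than they need to be

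*Protocol*

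**What the plan says.** Section 7.1.9 (Randomisation) describes the design: "Allocation will employ a stratified random permuted block method with stratification by severity of alcohol dependence", and also by "site and the prescription of other relapse prevention medication". It gives the reason: "These variables are known to be related to clinical outcomes and will be collected at preliminary screening".

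Section 7.2.4 (Data analysis) carries the strata into the primary effectiveness model: "Covariates included in the analysis will include stratification variables, gender and body weight". For the drinking outcomes it says "these will be adjusted for known confounders; SADQ, site, age and gender", which keeps site but not co-prescribed medication.

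Section 7.2.5 (Economic analysis) sets a separate list for the 12-month economic comparison: "Costs and QALYs will be adjusted for pre-specified baseline covariates (age, gender, alcohol dependence severity) including costs and utility values". The method is generalised linear modelling, missing cost and QALY data are multiply imputed, and decision uncertainty is shown by acceptability curves from a non-parametric bootstrap. Resource use is valued at national tariffs.

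Section 7.1.1.1 says of standard support: "The type, frequency and intensity of psychosocial intervention received vary between specialist alcohol services". The sentence goes on to say that care also varies between individuals, and that it depends on need and on what is funded and available locally.

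**The concern.** A trial that randomises within strata normally analyses by them. The strata were chosen as prognostic, and a model that leaves them out counts the variance between them as error. Here the effectiveness model follows that rule and the economic model does not, without explanation. Site is also the factor for which the protocol itself describes differences in the amount of care given, and that amount feeds directly into cost.

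Section 6 lists cost-effectiveness at 12 months among the primary hypotheses. What is at stake is precision: somewhat wide intervals for incremental cost and incremental QALYs, and acceptability curves that show somewhat more uncertainty than the design leaves. Two primary questions in one trial would also be adjusted for different design factors.

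**Working it through.** **Covariates side by side**

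| Factor | Randomisation (7.1.9) | Primary effectiveness (7.2.4) | Drinking outcomes (7.2.4) | Costs and QALYs (7.2.5) |
|---|---|---|---|---|
| Dependence severity | stratum | yes | yes | yes |
| Site | stratum | yes | yes | no |
| Other relapse-prevention medication | stratum | yes | no | no |

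The economic list also has age, gender, baseline costs and baseline utility.

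**The plan's own figure.** The protocol states no sample size or precision for the economic analysis. The only sample-size figure is for 6-month adherence (7.2.2): effect size 0.3, 80% power, two-sided 0.05, 2:1:1. With m per intervention arm and 2m in standard support, the variance factor is 1/m + 1/(2m) = 1.5/m. So m = 1.5 × (1.960 + 0.842)² / 0.3² = 130.9, rounded up to 131, which gives 262 + 131 + 131 = 524 as stated. Allowing for 30% attrition, 524 / 0.70 = 748.6, against 748 stated. The figures reproduce. They are used below only for the size of the trial.

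**Effect of omitting strata on interval width.** Let R² be the share of residual variance explained by site and other medication after the covariates already listed. In a linear model the ratio of interval width, omitted to included, is 1/√(1 − R²). For other generalised linear models this is an approximation. The documents give no R², so the range 0 to 0.10 is an assumption.

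| R² (assumed) | 1/√(1 − R²) | Excess width | Simulated ratio | Coverage, strata omitted | Coverage, strata included |
|---|---|---|---|---|---|
| 0 | 1.000 | 0% | 0.998 | 95.4% | 95.4% |
| 0.01 | 1.005 | 0.5% | not run | not run | not run |
| 0.02 | 1.010 | 1.0% | 1.009 | 94.3% | 94.1% |
| 0.05 | 1.026 | 2.6% | 1.024 | 95.2% | 94.8% |
| 0.10 | 1.054 | 5.4% | 1.052 | 95.4% | 94.5% |

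The simulation used 2,000 replicates per row, 748 randomised in permuted blocks of four at 2:1:1 within strata, five sites, 30% lost at random and a normal outcome. Site carried the whole assumed R². The Monte Carlo standard error of each coverage figure is √(0.95 × 0.05 / 2000), about 0.5 points, so coverage stays near the nominal 95% with or without the strata. The width ratios follow the formula.

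**Cost of adding the factors.** Five sites need four indicators and medication needs one, so about five degrees of freedom are used. On the 6-month figures each pairwise comparison has 262 + 131 = 393 analysed. If the strata explain nothing, the simulated penalty for including them is about 0.2% in width (1/0.998).

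**The case against.** The best counter-argument is that little variance may be left to recover. Baseline cost and baseline utility are already in the models and may absorb much of any site difference. National tariffs remove price differences, so sites differ only through volume of use. Services have agreed to follow the same guideline on prescribing. The protocol attributes variation in care to individuals as well as to services, and 7.1.9 links the strata to clinical outcomes, not to cost or EQ-5D. All of this stands. It is why the assumed range stops at 0.10 and why the widening is conditional. It does not explain why the list departs from the randomisation.

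It could also be said that such detail belongs in a later analysis plan. Section 7.2.5, however, names the covariates and calls them pre-specified, so the comment is on what is written. The resampling scheme is different: the protocol does not say that the bootstrap ignores the strata, so its silence there is not a defect.

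Three stronger readings are tempting, and the documents support none of them.

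- A reader might infer a sizeable loss of power or a distorted test. Section 7.2.5 states no power and no significance test for the economic outcomes, and the 80% power and 0.3 effect belong to 6-month adherence. Blocked stratification also already reduces the true sampling variance when the strata are left out of the model, so holding unadjusted power at 80% would overstate the gain from adjusting.
- A reader might infer a large effect from an R² of 0.20 or more. Nothing in the protocol supplies such a value, least of all after baseline cost and utility.
- A reader might infer bias. The arms are balanced on the strata by design, and nothing in the protocol suggests that the 30% attrition differs by arm within strata.

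**Conclusion.** The inconsistency is plain on the text: site and other relapse-prevention medication are randomisation strata and covariates in the primary effectiveness model, but they are absent from the pre-specified economic list without a stated reason. The consequence is a possible, conservative loss of precision. Interval width for incremental cost and QALYs is 0% to about 5% too large over an assumed residual R² of 0 to 0.10, and the acceptability curves inherit this. If the two factors explain nothing beyond the listed covariates, nothing is lost. The estimate rests on that assumed range and on a linear-model approximation. The severity is minor: the reasons to act are consistency with the design and the negligible cost.

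**What to change.** In 7.2.5, give both the cost and the QALY models the same design covariates: site, severity on the SADQ and prescription of other relapse-prevention medication, with age, gender and baseline cost or baseline utility. Generate the bootstrap for the ICERs and acceptability curves by resampling within arm and refitting these strata-adjusted models in each replicate. Resampling within arm and site alone would not be enough, because it ignores the other two strata.

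This is a change of a sentence or two. Both factors are collected at preliminary screening, so no new data or participants are needed, and the sample size is unchanged. If the omission was deliberate, one sentence giving the reason would settle the point.

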## **8. Storage of source data and confidentiality**

There are three sources of data collection for the current research project.

### **a. Data collection by the research team.**

Research and personal data will be collected using electronic data capture, specifically designed for this research study by Codeface Ltd, using a laptop or desktop computer with wireless (3G or WiFi) connection. Laptop computers will be password protected. Data will sent to a secure server with a 256bit encryption (SSL/https) connection, no data will be saved directly onto the laptop computer.

Research data will be anonymised by assigning each participant a unique ID number, personal data will be stored separately to the anonymised research data to maintain participant anonymity.

- b. Delivery of the intervention and data collection by pharmacists based in a central telephone support service

A secure electronic patient management system, developed and maintained by Partizan Health, will be used to facilitate delivery of the medication management and contingency management interventions. This is a Cloud based system, all data is stored in the UK and meets the European Medicines Agency and the Food and Drug Administration requirements for handling patient Identifiable Information. SSL Cryptography for the transmission of data to/from the application layer and also to/from the database. All data will be encrypted with AES CBC encryption on the database. All study data will be transferred securely to the research team either via encrypted memory stick/email or extracted directly from the patient management system by the research team.

- c. Audio recording of the intervention delivery by Celesio

All telephone calls are audio recorded and securely stored by Celesio as part of routine practice. Audio files will be securely transferred to the research team via email or direct downloading of the files from Celesios system.

All audio files and participant data will be stored on King's College London's secure server accessible by the research team via password protected computers only.

Identifiable patient information will be accessed by the clinical staff and information will be passed on to the research team with the patient's consent. Consent to take part in the study will also be completed electronically, overseen by a trained researcher, participants will be given the opportunity to receive a copy of the consent form. All data for analysis will be stored under code numbers so that no personal data can be obtained from it. Members of the research team will have access to participants' personal data in order to establish contact for the follow-up interviews. This will be explained in the information provided to potential participants. At the end of the study arrangements will be made with the appropriate data repository service for transfer and preservation of the data in accordance with the principles agreed by the NHS/NIHR for the preservation and sharing of clinical data.

## **9. Publication policy**

Publication of the trial results will be the responsibility of the chief investigator

## **10. Safety reporting**

A Serious Adverse Event (SAE) is defined as an untoward occurrence that;

- a. Results in death;
- b. Is life threatening
- c. Requires hospitalisation or prologation of an existing hospital stay;
- d. Results in persistent or significant disability or incapacity;
- e. Consists of a congenital anomaly or birth defect; or
- f. Is otherwise considered medically significant by the investigator.

The Chief Investigator will report an SAE to the Research Ethics Committee (REC) who provided favourable ethical opinion within 15 days of becoming aware of the event if the event is related (that is, resulted from administration of any of the research procedures), and unexpected (that is, the type of event is not listed in the protocol as an expected occurrence).

If an urgent safety measure is required, the Chief Investigator will immediately by telephone and then in writing within 3 days inform the REC who gave favourable ethical opinion the reasons for the urgent safety measures and the plan for further action.

The Chief Investigator will report on the safety of participants in annual progress report to the REC.

### **11. Ethical considerations**

Regulatory approvals: The trial will be conducted in compliance with the principles of the Declaration of Helsinki (1996) and Good Clinical Practice (GCP) and in accordance with all applicable regulatory requirements including but not limited to the Research Governance Framework (Department of Health, 2008). This protocol and related documents will be submitted for review to the appropriate Research Ethics Committee (REC) and R&D management approval will be gained for all trial sites before the commencement of the research.

Consent: All participants will be given written information about the trial including the risks and benefits of taking part. In line with GCP, participants will be given ample opportunity (i.e. at least 24 hours) to ask any questions about the trial and its procedures. Participants' right to decline participation and withdraw from the research without it affecting their clinical care will be made clear. Consent will be collected electronically by a trained researcher before any trial related procedures take place by a member of the research team. Participants will be given the opportunity to receive a copy of the consent form.

Prescription of acamprosate: The decision to prescribe acamprosate will be made by the treating clinician of the specialist alcohol service in conjunction with the service user as part of their treatment plan.

Study questionnaires: There may be some psychological discomfort resulting from completion of the trial specific questionnaires and interviews, for example, regarding alcohol habits and associated problems and psychiatric disorders. However, the potential benefit to the service users health of improved adherence to acamprosate outweighs any minor transient discomfort experienced from completing the questionnaires/interviews.

Contingency Management: Vouchers for retailers that are not licenced to sell alcohol will be provided as incentives in the CM arm of the trial.

Honorarium: At each research appointment (initial assessment, 6 and 12 month follow-up) all participants will be given £10 cash to compensate them for their time and travel expenses.

Researcher risks: There are potential risks of aggression in intoxicated patients. However, the researchers will be experienced in clinical research with this population and appropriate NHS and university risk management policies will be employed.

Confidentiality: Participants anonymity will be preserved throughout by the use of code numbers for all data collection. Data will be anonymised and be stored by secure means (password protected computers/laptops, locked filing cabinets in lockable offices in buildings with swipe access and security presence) in accordance with Good Clinical Practice and King's College London's Standard Operating Procedures.

Conflict of interest: All participants will have access to the standard care provided by the specialist alcohol health service, therefore participation will not have any detrimental effects on the care received by the patient. This will be made clear to potential participants prior to requesting informed consent.

Information about results of study: During initial interviews and informed consent, patients will be told that the findings of the research can be requested to be sent to them in their preferred way (e.g. post, email, telephone) and that they are welcome to contact the research team to discuss the findings and ask any questions they have regarding the research and their participation.

